## **2. STUDY OBJECTIVES AND ENDPOINTS**

### **2.1. Objectives**

#### **2.1.1. Primary Objectives**

- To determine the safety and efficacy of fesoterodine 4 mg and 8 mg following once daily treatment for 12 weeks in pediatric NDO subjects with weight  $>25$  kg.
- To determine the safety and efficacy of fesoterodine 2 mg and 4 mg following once daily treatment for 12 weeks in pediatric NDO subjects with weight  $\leq 25$  kg.

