#### *Cohort 1 (Subjects >25 kg)*

For this cohort this is a randomized, open label, active comparator parallel group study with three treatment arms.

Note: The first week of the fesoterodine 8 mg group will be at a dose of 4 mg each day, for the active comparator phase and for those subjects changing from oxybutynin to the safety extension phase.

[figure not shown]
The study consists of two parts: a 12 week three arm phase with an active comparator (oxybutynin XL), followed by a 12 week two arm extension phase without the active comparator.

There is a variable screening period (minimum 3 days) prior to the baseline visit, the duration of which is principally determined by the prior medication subjects may need to washout ([Appendix 3](#)). At baseline, subjects will be randomized to one of three arms: 4 mg or 8 mg/day of fesoterodine or oxybutynin XL. Subjects will be randomized to each arm in a 1:1:1 ratio.

After 12 weeks (or earlier if appropriate), subjects in the oxybutynin arm of the study will be allocated by the investigator to fesoterodine at either 4 mg or 8 mg/day.

A sufficient number of subjects will be randomized into Cohort 1 to ensure a total of approximately 99 subjects (approximately 33 evaluable subjects per arm) are evaluable for the primary efficacy and safety analyses at Week 12, after which screening to Cohort 1 will be closed.

*Cohort 2 (Subjects  $\leq 25$  kg)*

Note: The first week of the fesoterodine 4 mg group will be at a dose of 2 mg each day, for the efficacy phase.

For this cohort the study consists of two parts: a 12 week two arm efficacy phase, followed by a 12 week two arm safety extension phase.

There is a variable screening period (minimum 3 days) prior to the baseline visit, the duration of which is principally determined by the prior medication subjects may need to washout ([Appendix 3](#)).

At baseline, subjects will be randomized to one of two fesoterodine treatment arms: doses 2 mg and 4 mg/day). Subjects will be randomized to each arm in a 1:1 ratio. Once allocated subjects will remain on that dose for the 12 week efficacy phase, and will continue at the same dose during the 12 week safety extension phase.

It is planned that a sufficient number of subjects will be randomized into this cohort to ensure a total of approximately 50 subjects (approximately 25 evaluable subjects per arm) are evaluable for the primary efficacy and safety analyses at Week 12, after which screening to Cohort 2 will be closed.

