### **9.3. Safety Analysis**

The Safety Analysis Set will be defined separately for each cohort and consists of all randomized subjects who have received at least one dose of study medication in the relevant phase of the study.

For each cohort, results from the safety assessments and any adverse events will be presented in tabular and/or graphical format adhering to current [Pfizer Data Standards](#). These presentations will be split by treatment group, and produced separately for the active comparator/efficacy phase and the safety extension phase. Safety endpoints such as vital signs, laboratory evaluations, weight, PVR, vision testing and CBCL/GPT results will be presented descriptively by treatment group. Adverse event incidence rates will be compared descriptively between treatment arms. An evaluation of withdrawal rates and time to withdrawal will be performed.

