#### **Three Tier Adverse Event Reporting**

The presentations described in this section will only concern treatment emergent adverse events which occurred during the active comparator/efficacy phases of this study for each cohort, and will be presented separately for each cohort. The active comparator/efficacy phase is defined as first dose to week 12 plus a lag time of 7 days.

Where presented, for Cohort 1, the treatment comparisons will be Fesoterodine 4mg vs. Oxybutynin and Fesoterodine 8mg vs. Oxybutynin. The risk difference will be calculated as Fesoterodine (4mg PR or 8mg PR) minus Oxybutynin. There will be no treatment comparisons presented for Cohort 2, as there is no active comparator for this cohort.

Adverse events will be presented in order of system organ class.

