#### Tier 1 Adverse Event Reporting

Tier 1 summaries will only report those adverse events which have been identified as targeted medical events (TMEs) in the safety review plan.

The percentage of subjects experiencing a particular adverse event in each treatment group will be presented both in a table and graphically. The table will present the point estimate for the percentage of affected subjects, along with risk differences, their 95% confidence intervals and p-values, for Cohort 1 (fesoterodine 4mg PR or 8mg PR minus Oxybutynin). However for Cohort 2, only point estimates will be presented, as there is no active comparator for this cohort.

Graphical presentations will include the point estimate for the percentage of affected subjects, along with the risk differences and their 95% confidence intervals for Cohort 1, and point estimates only for Cohort 2.

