### Tier 2 Adverse Event Reporting

Tier 2 summaries will only report those adverse events which occurred to 4 or more subjects in any treatment group.

The percentage of subjects experiencing a particular adverse event in each treatment group will be presented both in a table and graphically. The table will present the point estimate for the percentage of affected subjects, along with the risk differences and their 95% confidence intervals, for Cohort 1. However for Cohort 2, only point estimates will be presented, as there is no active comparator for this cohort.

Graphical presentations will include the point estimate for the percentage of affected subjects, along with the risk differences and their 95% confidence intervals for Cohort 1, and point estimates only for Cohort 2.

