### Tier 3 Adverse Event Reporting

Tier 3 adverse events are events that are neither tier-1 nor tier-2 events, however these will not be summarized separately. All adverse events (Tier 1, 2 and 3 adverse events) will be presented together in table form only. The frequency and percentage of subjects will be presented by treatment group.

It should be recognized that most studies are not designed to reliably demonstrate a causal relationship between the use of a pharmaceutical product and an adverse event or a group of adverse events. Except for select events in unique situations, studies do not employ formal adjudication procedures for the purpose of event classification. As such, safety analysis is generally considered as an exploratory analysis and its purpose is to generate hypotheses for further investigation. The 3-tier approach facilitates this exploratory analysis.

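### The Cohort 2 adverse-event tables omit the 4 mg minus 2 mg risk difference and its 95% interval, for a reason that does not apply to two randomised doses

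*SAP*

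**What the plan says.** Safety of the two Cohort 2 doses is part of a primary objective: "To determine the safety and efficacy of fesoterodine 2 mg and 4 mg following once daily treatment for 12 weeks" (Protocol 2.1.1). In the Cohort 2 part of Protocol section 3, allocation is to two fesoterodine doses, and "Subjects will be randomized to each arm in a 1:1 ratio".

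Protocol 9.3, in a paragraph that applies to each cohort, says: "Adverse event incidence rates will be compared descriptively between treatment arms".

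SAP 8.2.5 treats the cohorts differently:

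- Three Tier Adverse Event Reporting: each Cohort 1 fesoterodine dose is contrasted with oxybutynin. For the other cohort, "There will be no treatment comparisons presented for Cohort 2, as there is no active comparator for this cohort".
- Tier 1 (targeted events): Cohort 1 gets risk differences, 95% intervals and p-values. "However for Cohort 2, only point estimates will be presented, as there is no active comparator for this cohort".
- Tier 2: "Tier 2 summaries will only report those adverse events which occurred to 4 or more subjects in any treatment group". Percentages are shown "along with the risk differences and their 95% confidence intervals, for Cohort 1", and Cohort 2 again gets point estimates only.
- Tier 3: all events go into one table, and "The frequency and percentage of subjects will be presented by treatment group".

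Other Adverse Event Reporting then gives events by dose for the efficacy phase, the extension and the full 24 weeks. No contrast between fesoterodine doses is planned in either cohort.

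**The concern.** The reason given is that Cohort 2 lacks an active comparator. That explains why no comparison with oxybutynin can be made. It does not explain why one randomised dose is not compared with the other.

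Cohort 2 has no untreated or comparator group, so each arm's percentage combines drug effect with whatever background illness these children have. The 4 mg versus 2 mg contrast is the only randomised safety contrast available at 25 kg or less. With two bare percentages from about 25 children each, a chance gap may be read as dose-related harm, or a real gap may be dismissed, because nothing shows how precise the gap is. The words that forbid treatment comparisons also leave it unclear how the descriptive comparison in Protocol 9.3 is to be delivered.

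**Working it through.** **The plan's own figure.** Neither document gives a precision or power figure for adverse events. The only Cohort 2 precision figure is for efficacy (Protocol 9.1): about ±55 mL with 25 per arm, SD 120 mL and 80% coverage probability. It reproduces: t(0.975, 24) × SD × √(χ²(0.80, 24)/24) / √n = 2.064 × 120 × √(29.55/24) / 5 = 54.97 mL. It is not in dispute and does not bear on adverse events.

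**Inputs.** 25 evaluable per arm in Cohort 2 and 33 per arm in Cohort 1 (Protocol 9.1). No paediatric event rates are given, so rates are assumed over a range. One illustrative pair uses the adult dry-mouth incidences in Protocol 1.2, 19% at 4 mg and 35% at 8 mg. These come from adults and mostly from other doses, and serve only to show scale.

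**Precision of the omitted difference.** Wald 95% half-width = 1.96 × √[(p₁(1−p₁) + p₂(1−p₂))/n]

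| Rates assumed | n per arm | Half-width |
|---|---|---|
| 10% and 10% | 25 | 1.96 × √(0.18/25) = 0.166 |
| 20% and 20% | 25 | 1.96 × √(0.32/25) = 0.222 |
| 50% and 50% | 25 | 1.96 × √(0.50/25) = 0.277 |
| 19% and 35% | 25 | 1.96 × √(0.3814/25) = 0.242 |
| 19% and 35% | 33 | 1.96 × √(0.3814/33) = 0.211 |

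So the range is about ±17 to ±28 points in Cohort 2. At the same assumed rates, Cohort 2 is about 3 points less precise than Cohort 1 (±24 against ±21), where the SAP does show intervals.

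**How often the interval would exclude zero.** Exact binomial enumeration of the Newcombe interval at 19% versus 35% gives 26% of trials with 25 per arm and 32% with 33 per arm. The display would quantify uncertainty. It would not be a sensitive detector of gaps of this size.

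**What the interval adds.** Newcombe limits, with d = p₁ − p₂ and Wilson limits (l, u) for each arm: lower = d − √[(p₁−l₁)² + (u₂−p₂)²]; upper = d + √[(u₁−p₁)² + (p₂−l₂)²].

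- 9/25 versus 5/25: Wilson limits 0.202 to 0.555 and 0.089 to 0.391. d = 0.16, interval −0.09 to +0.38.
- 10/25 versus 3/25: Wilson limits 0.234 to 0.593 and 0.042 to 0.300. d = 0.28, interval +0.04 to +0.49.

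The first interval includes zero and the second does not. The percentages alone (36% and 20%; 40% and 12%) do not tell the reader that.

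**Chance exclusions.** With equal 20% rates and 25 per arm, enumeration gives about 5% of Newcombe intervals excluding zero. If 20 independent terms were shown (an assumption), at least one would do so in 1 − 0.95²⁰ = 64% of trials.

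**The case against.** A reader might infer that dose-related harm in Cohort 2 is never estimated. The documents do not support that. Each arm's percentage is tabulated and plotted for Tier 1 and Tier 2 events, all events are tabulated by treatment group, and events are reported by dose in each phase and over 24 weeks. The difference is one subtraction away, and a reader with the counts could compute the interval.

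A reader might also infer that the SAP bars every between-arm comparison and so breaches the protocol. That is too strong as well. The sentence governs the presentations in the three-tier section. Protocol 9.3 promises only a descriptive comparison, with no risk difference or interval, and side-by-side percentages largely meet it. The opening of Protocol section 9 allows the SAP to modify the plans, and requires an amendment only for major changes to the primary endpoint or its analysis. What stands is that the wording is misaligned and the reason given is wrong.

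The sponsor could add that no objective asks for a dose contrast: the only comparative objective is fesoterodine versus oxybutynin, and Cohort 2 efficacy is also assessed within arm. That is fair. It makes the omission a weakness of presentation, not a failure to estimate a planned quantity.

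Finally, unadjusted intervals over many terms will produce chance exclusions. This is true, but it applies equally to the intervals that the SAP already shows for Cohort 1, and the Tier 3 text already describes safety analysis as exploratory.

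**Conclusion.** The point holds as a minor reporting gap. For Cohort 2 the SAP omits the displayed 4 mg minus 2 mg risk difference and its 95% interval. It justifies this by a condition that two doses randomised 1:1 do not need, in words that do not match the descriptive comparison in Protocol 9.3. What the reader loses is the uncertainty of the difference, not the difference itself.

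The omitted interval would be about ±17 to ±28 points with 25 per arm, for assumed rates of 10% to 50%. Small numbers do not explain the different treatment of the cohorts, since the gap in precision is about 3 points at the illustrative 19% and 35%. Nor should the interval be oversold: at those rates it would exclude zero in about a quarter of trials. All of these sizes rest on assumed event rates, because the documents give none for this population. No efficacy conclusion is affected.

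**What to change.** In SAP 8.2.5, replace the sentence on Cohort 2 in Three Tier Adverse Event Reporting, and the matching point-estimate-only statements for tables and plots under Tier 1 and Tier 2, with text such as:

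> For Cohort 2, Tier 1 and Tier 2 tables and plots will present the risk difference, fesoterodine 4 mg BIC minus 2 mg BIC, with a 95% score-type (e.g. Newcombe) confidence interval, without p-values, as a descriptive, exploratory comparison.

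This brings the SAP into line with Protocol 9.3. Optionally, add the 8 mg PR minus 4 mg PR difference with its 95% interval to the Cohort 1 tables, where the dose contrast is also absent.

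The cost is a wording change and an extra column in a layout that the SAP already specifies for Cohort 1. No new data or participants are needed. The downside is that the intervals will be wide and unadjusted across terms, so some will exclude zero by chance. A footnote in each output should say so and label the intervals exploratory.

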#### Tier 1 Adverse Event Reporting

Tier 1 summaries will only report those adverse events which have been identified as targeted medical events (TMEs) in the safety review plan.

The percentage of subjects experiencing a particular adverse event in each treatment group will be presented both in a table and graphically. The table will present the point estimate for the percentage of affected subjects, along with risk differences, their 95% confidence intervals and p-values, for Cohort 1 (fesoterodine 4mg PR or 8mg PR minus Oxybutynin). However for Cohort 2, only point estimates will be presented, as there is no active comparator for this cohort.

Graphical presentations will include the point estimate for the percentage of affected subjects, along with the risk differences and their 95% confidence intervals for Cohort 1, and point estimates only for Cohort 2.

### Tier 2 Adverse Event Reporting

Tier 2 summaries will only report those adverse events which occurred to 4 or more subjects in any treatment group.

The percentage of subjects experiencing a particular adverse event in each treatment group will be presented both in a table and graphically. The table will present the point estimate for the percentage of affected subjects, along with the risk differences and their 95% confidence intervals, for Cohort 1. However for Cohort 2, only point estimates will be presented, as there is no active comparator for this cohort.

Graphical presentations will include the point estimate for the percentage of affected subjects, along with the risk differences and their 95% confidence intervals for Cohort 1, and point estimates only for Cohort 2.

### Tier 3 Adverse Event Reporting

Tier 3 adverse events are events that are neither tier-1 nor tier-2 events, however these will not be summarized separately. All adverse events (Tier 1, 2 and 3 adverse events) will be presented together in table form only. The frequency and percentage of subjects will be presented by treatment group.

It should be recognized that most studies are not designed to reliably demonstrate a causal relationship between the use of a pharmaceutical product and an adverse event or a group of adverse events. Except for select events in unique situations, studies do not employ formal adjudication procedures for the purpose of event classification. As such, safety analysis is generally considered as an exploratory analysis and its purpose is to generate hypotheses for further investigation. The 3-tier approach facilitates this exploratory analysis.

### **Other Adverse Event Reporting**

Adverse events will be reported separately for the active comparator phase, the safety extension phase and over the entire study. Summaries will be presented as follows:

For the Active Comparator/Efficacy Phase:

The active comparator/efficacy phase is defined as the first dose up to week 12 if the subject continues into the Safety Extension Phase. If a subject has discontinued early during the active comparator/efficacy phase, the reporting period for this phase will be up to their last dose of study medication plus the drug specific lag time. For Fesoterodine this will be 7 days, however for Oxybutynin (Cohort 1 only) this will be either 2 days or the time until first treatment of Fesoterodine in the safety extension phase, whichever is longer. The following treatment groups will be summarized.

Cohort 1:

Fesoterodine 4mg PR

Fesoterodine 8mg PR

Oxybutynin

Cohort 2:

Fesoterodine 2mg BIC

Fesoterodine 4mg BIC

For the Safety Extension Phase:

The safety extension phase is started after the first dose of fesoterodine in the safety extension phase is administered. Only adverse events that started or worsened in the Safety Extension phase would be counted as treatment emergent in this phase. Note that treatment emergent AEs will be defined as described in the Pfizer Data Standards for cross over studies. The following treatment groups will be summarized.

Cohort 1:

Oxybutynin -> Fesoterodine 4mg PR

Oxybutynin -> Fesoterodine 8mg PR

Fesoterodine 4mg PR -> Fesoterodine 4mg PR

Fesoterodine 8mg PR -> Fesoterodine 8mg PR

Cohort 2:

Fesoterodine 2mg BIC -> Fesoterodine 2mg BIC

Fesoterodine 4mg BIC -> Fesoterodine 4mg BIC

For the whole study (overall):

These presentations will only include subjects who were randomised to fesoterodine.

Cohort 1:

Fesoterodine 4mg PR (24 weeks)

Fesoterodine 8mg PR (24 weeks)

Cohort 2:

Fesoterodine 2mg BIC (24 weeks)

Fesoterodine 4mg BIC (24 weeks)

Plots displaying the point estimate for the percentage of subjects in each treatment group who experience adverse events of particular interest will be presented for the Safety Extension phase and for the study as a whole.

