### **5.2. Oxybutynin (Subjects >25 kg)**

Subjects in Cohort 1 (weight >25 kg) randomized to oxybutynin will receive oxybutynin extended release (XL) tablets at a starting dose in accordance with approved pediatric labeling, and accepted practice eg, oxybutynin XL 5 mg once a day. Dose optimization will be achieved by either up or down titration in 5 mg increments on an approximately weekly basis to achieve a balance of efficacy and tolerability. All subjects should achieve a minimum total daily dose of oxybutynin XL 10 mg by the end of the dose adjustment period

at Week 4. The maximum dose used in this study will not exceed the recommended dose consistent with approved pediatric labeling, and accepted practice. Subjects who were on oxybutynin prior to study entry and who are randomized to the oxybutynin XL treatment group may, at the discretion of the investigator, restart at the equivalent pre-study total daily dose.

After Week 4, subjects taking oxybutynin XL should remain on the same dose for the subsequent 8 weeks of the study, and no further dose adjustments should be permitted. Subjects who are unable to tolerate a minimum total dose of oxybutynin XL 10 mg once daily should be withdrawn. Subjects who withdraw from the oxybutynin treatment arm for reasons of toleration, and who fulfill all continuation criteria, may be directly allocated by the investigator to fesoterodine treatment at either 4 mg or 8 mg/day for the remaining 12 week safety extension period. All those assigned to the fesoterodine 8 mg arm will start at 4 mg daily for one week, and will then escalate to 8 mg daily. All subsequent study visits should be scheduled relative to the start of the extension phase.

At Visit 5 (or earlier if appropriate), subjects in the oxybutynin arm of the study will be allocated by the investigator to fesoterodine at either 4 mg or 8 mg/day. Subjects should undergo a minimum 2 day washout period from oxybutynin prior to starting treatment with Fesoterodine. All those assigned to the fesoterodine 8 mg arm will start at 4 mg daily for one week, and will then escalate to 8 mg daily. Once allocated the dose will remain fixed for the period of the extension; if treatment is inadequate or the subject cannot tolerate the dose, consideration should be given to withdrawal.

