| 1.2
14 Apr 2014 | PA 5
3 Mar 2014 | Protocol amended to include lighter weight cohort (Cohort 2 - subjects $\leq 25$ kg), originally planned to be studied under a separate protocol (A0221074). | 
 
The SAP has been amended to describe the analyses for Cohort 2. The intention is to analyse and summarize each cohort separately, therefore additional sections have been added into the SAP specifically to describe the Cohort 2 analyses and summaries.
 
   |
| 2.0
25 Feb 2020 | N/A                | Prior to DB Release  | 
 
Removal of figures and listings that have been removed from the List of Tables (LOT) as part of the TLF reduction exercise. The data presented in the figures that have been removed are presented in tables.
 
Exploratory analyses and subgroup figures removed as these won't be included in the CSR. Some have been replaced by descriptive subgroup summary tables instead.
 
As some subjects will only record micturitions in their bladder diary (if they are not catheterizing) and some will only record catheterizations (if they only catheterize), these two endpoints will only be calculated for subjects with <math>>0</math> episodes at baseline.
 
Section 8.2.5 (Other Adverse Event Reporting) has been updated to clarify that the lag period is only applied if a subject discontinues study medication in the Active Comparator/ Efficacy Phase (otherwise, for subjects who continue into the Safety Extension AEs could be counted twice).
 
Other minor updates to ensure SAP is aligned with how results are being presented in tables, figures and listings.
 
 |

The study is ongoing, and unblinded data from the study have been reviewed by an External Data Monitoring Committee; however that review has not influenced any of the changes documented in this amendment.

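### In the SAP's by-phase adverse event tables, events starting in the oxybutynin washout of subjects who complete Week 12 and continue fall in no phase, and non-switching early stoppers get a shorter lag on oxybutynin (2 days) than on fesoterodine (7)

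*SAP*

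**What the plan says.** SAP 8.2.5, Other Adverse Event Reporting, sets the windows for the by-phase tables.

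- Subjects who continue: "The active comparator/efficacy phase is defined as the first dose up to week 12 if the subject continues into the Safety Extension Phase". The version 2.0 entry in SAP Table 1 confirms that they get no lag, since "the lag period is only applied if a subject discontinues study medication in the Active Comparator/ Efficacy Phase". The reason given is to avoid counting an event twice.
- Subjects who stop early: "the reporting period for this phase will be up to their last dose of study medication plus the drug specific lag time". The lag differs by drug: "For Fesoterodine this will be 7 days", while for oxybutynin it is "either 2 days or the time until first treatment of Fesoterodine in the safety extension phase, whichever is longer".
- Extension phase: "The safety extension phase is started after the first dose of fesoterodine in the safety extension phase is administered". Only events that start or worsen in that phase count there.
- Whole-study tables: "These presentations will only include subjects who were randomised to fesoterodine".

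Between the two treatments, Protocol 5.2 requires a gap: "Subjects should undergo a minimum 2 day washout period from oxybutynin prior to starting treatment with Fesoterodine". No maximum is stated.

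SAP 8.2.5, Three Tier Adverse Event Reporting, uses a different window for the same phase: first dose to week 12 plus 7 days, in every arm. The fesoterodine-minus-oxybutynin risk differences and confidence intervals are in those tables, with p-values for Tier 1.

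**The concern.** The by-phase rules leave an interval that belongs to nobody, and only oxybutynin subjects have it. At Visit 5 a completer is normally still on oxybutynin (Protocol 7.1.1 asks for urodynamics about 4-6 hours after a dose, when possible). The subject then washes out before fesoterodine starts. If week 12 means the Visit 5 date, the comparator phase has closed and the extension has not opened. A subject staying on fesoterodine has no washout and no such interval.

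The SAP treats the same days differently for a subject who leaves oxybutynin early and switches: there the window runs to the first fesoterodine dose, so washout events count under oxybutynin. Nothing explains why a completer's washout events should not.

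The second difference concerns early stoppers who never switch. They are followed for 5 days less on oxybutynin than on fesoterodine, with no reason given beyond calling the lag drug specific.

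Comparative safety against oxybutynin is a secondary objective (Protocol 2.1.2), so adverse events should not drop out of the by-phase tables in one arm because of how windows are drawn.

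**Working it through.** The plan gives no figure of its own on this point, so the check is window arithmetic followed by a sizing under stated assumptions.

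**Inputs from the documents**
- Continuers: comparator phase closes at week 12 (12 × 7 = 84 days), no lag; extension opens at first extension fesoterodine dose (SAP 8.2.5).
- Washout w of at least 2 days (Protocol 5.2).
- Early-stop lag: 7 days on fesoterodine; the larger of 2 and w on oxybutynin, or 2 if the subject never switches (SAP 8.2.5).
- Three-tier window: week 12 plus 7 days, all arms (SAP 8.2.5).
- 33 evaluable subjects per arm (SAP 4.1).

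**Assumptions, not in the documents**
- Week 12 is the last oxybutynin dose date.
- All 33 oxybutynin subjects complete and continue (for the gap).
- 12-week incidence p between 10% and 70%, constant hazard.
- For the lag, 5% to 30% of the arm stops at day 42 without switching.

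**Step 1: days after last oxybutynin dose, subjects entering the extension**

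| Washout w | Completer, by-phase: uncovered (w) | Early switcher, by-phase: uncovered | Three-tier, completer: uncovered max(0, w−7) | Three-tier, completer: overlap with fesoterodine max(0, 7−w) |
|---|---|---|---|---|
| 2 | 2 | 0 | 0 | 5 |
| 7 | 7 | 0 | 0 | 0 |
| 10 | 10 | 0 | 3 | 0 |

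At the minimum washout the uncovered time is 33 × 2 = 66 person-days, or 2/84 = 2.4% of the comparator phase.

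**Step 2: early stoppers who never switch**

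7 − 2 = 5 days shorter on oxybutynin. For a stop at day 42, follow-up is 44 days against 49, which is 5/49 = 10% less. Protocol Appendix 3 does not explain the direction: it lists a half-life of 12-13 h for oxybutynin XL and about 7 h for fesoterodine, with the same 3-day minimum washout for both. Two days is 48/13 = 3.7 to 48/12 = 4.0 half-lives of oxybutynin XL; 7 days is 168/7 = 24 of fesoterodine.

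**Step 3: size of the washout gap**

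With S(t) = (1 − p)^(t/84), the share newly affected in the gap is S(84) − S(84 + w).
- w = 2, p = 10%: 0.9 × (1 − 0.9^(2/84)) = 0.0023, or 0.23 points; 33 × 0.0023 = 0.07 subjects.
- w = 2, p = 70%: 0.3 × (1 − 0.3^(2/84)) = 0.0085, or 0.85 points; 0.28 subjects. The curve peaks just inside the range, at p of about 63%: 0.372 × (1 − 84/86) = 0.0087, or 0.87 points.
- w = 7: 0.79 points (0.26 subjects) at p = 10% and 2.86 points (0.95 subjects) at p = 70%; peak 0.383 × (1 − 84/91) = 0.0294, or 2.9 points.

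**Step 4: size of the lag difference**

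With a share f stopping at day 42, the loss is f × [S(44) − S(49)].
- f = 5%, p = 10%: 0.05 × (0.9463 − 0.9404) = 0.0003, or 0.03 points; 0.01 subjects.
- f = 30%, p = 70%: 0.30 × (0.5322 − 0.4954) = 0.011, or 1.1 points; 0.36 subjects.

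**The case against.** The strongest objection is that the comparison that matters is elsewhere. A reader might infer that the fesoterodine-oxybutynin safety comparison is biased so that oxybutynin looks safer. The documents do not support that. The risk differences are in the three-tier tables, whose window is the same in every arm and covers a completer's washout of up to 7 days. With a 2-day washout it also takes in about 5 days of extension fesoterodine, which works the other way. The by-phase tables have no specified between-arm test, and the SAP regards safety analysis as generally exploratory. This part stands and limits the point to descriptive tables.

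A reader might also infer that every early oxybutynin stopper is followed for only 2 days. That overlooks the whichever-is-longer clause: those who switch to extension fesoterodine have their whole washout counted under oxybutynin.

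Other objections stand in part.
- For continuers, the by-phase comparator window closes at week 12 in both drugs. The gap therefore loses events; it does not make those two windows unequal.
- An event that starts in washout and worsens after the first extension dose is counted in the extension.
- Treatment emergence in the extension follows a sponsor standard for cross-over studies that is not in the documents. It might assign washout events, but it is cited only for the extension and cannot be assumed to close the gap.
- Week 12 is not defined as the nominal day or the Visit 5 date. Visit 5 may fall from 7 days early to 14 days late (Protocol 6.7), and SAP Appendix B sets no visit windows. On a nominal reading, an early Visit 5 can put the washout inside the comparator phase.
- A 2-day lag matches the minimum washout in Protocol 5.2, and 3.7 to 4.0 half-lives leaves little drug (1 − 2^−3.7 = 92% to 1 − 2^−4 = 94% eliminated). That makes 2 days defensible in itself, but does not explain why fesoterodine gets 7.
- A subject who completes Week 12 but does not continue fits neither window sentence cleanly. The Table 1 wording may cover this case, and the ambiguity is the same in all arms, so it has no direction.

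**Conclusion.** The point holds for the by-phase tables under Other Adverse Event Reporting only. With the last oxybutynin dose around Visit 5 and week 12 read as that visit, washout-onset events of oxybutynin subjects who complete and continue, and that do not later worsen, are in neither phase nor in the whole-study tables. Oxybutynin early stoppers who never switch are counted for 5 days less than their fesoterodine counterparts, without a stated reason.

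Both rules lower oxybutynin counts, but only slightly: about 0.2 to 0.9 percentage points for a 2-day washout, up to about 3 for a 7-day one, and about 0.03 to 1.1 for the lag. These sizes rest on assumed event and stopping rates and a constant hazard; a cluster of events just after stopping would make them larger. The primary efficacy result is untouched, and the three-tier risk differences are not under-counted in this way. The change is worth making because the SAP already treats early switchers correctly and no new data are needed.

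**What to change.** In SAP 8.2.5:

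1. For every oxybutynin subject who enters the extension, completer or early switcher, run the by-phase comparator window up to, but not including, the first extension fesoterodine dose, whatever the washout length. This also settles which rule applies to an early switcher, who now meets both, and still counts no event twice.
2. For subjects in any arm who stop in the comparator/efficacy phase, or complete it without continuing, and never enter the extension, use the same 7-day lag after last dose.
3. State whether week 12 means the Visit 5 date or the nominal day.
4. Reconcile the three-tier window with the by-phase window by cutting it at the first extension dose for subjects switching from oxybutynin.

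The cost is SAP wording and a small derivation change. The events are already recorded through the last subject visit (Protocol 8.2), with a contact about 2 weeks after stopping for withdrawals (Protocol 6.12). By-phase oxybutynin counts may rise slightly, and the completers' window becomes longer than that of fesoterodine continuers by the washout (2.4% for 2 days). In the three-tier tables, the cut removes fesoterodine days from the oxybutynin arm but leaves switchers with less time after week 12 than fesoterodine continuers (2 days against 7 for a 2-day washout). A table footnote should state both differences.
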